Hair Cortisol Measurement: Participants will be asked to provide hair samples to measure potential changes in cortisol (“stress hormone”); this method has been used successfully in stress studies²⁹⁻³¹ and is currently being utilized in another 3RP study [name] is involved in (Partners IRB Protocol #: 2016P001622). Hair grows roughly 1cm/month, thus ensuring sufficient growth for collection. The RA will mail detailed sampling instructions (Appendix 8.8) and stamped, addressed envelopes to facilitate returns. Participants will be instructed to provide one hair sample at baseline and one sample at the one-month follow-up. Specifically, they will be instructed to cut a small sample of hair (approximately 150 strands, about the diameter of a pencil eraser) from the back of their head, as close to the scalp as possible. They will be asked to tie the strands near the scalp end, place the sample in aluminum foil, and mail to MGH. The hair sampling instructions also include 6 questions about hair care, exercise, and glucocorticoid use, as these can affect hair cortisol measurements. Hair samples will not be collected from participants who have taken glucocorticoid medications (e.g. prednisone) within the past 3 months, as these medications cause cortisol measurements to be inaccurate. However, hair that is chemically treated or dyed may still be used for hair cortisol analysis. We will track the reasons why any hair samples were not collected, as this affects the feasibility and acceptability of hair cortisol analysis.

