5.5.3 Special Concerns

Some participants may feel uncomfortable sending us a hair sample; participants will not be required to participate in the hair sample collection if they feel uncomfortable or are otherwise unable to provide a hair sample. Participants can still remain in the study if they do not wish to complete a hair cortisol sample. Additionally, some subjects may not wish to participate in the weekly 3RP Session Evaluation Surveys or a qualitative exit interview for the study; these components of the study will be considered optional.

5.5.4 Compensation.

Subjects will receive \$10 in remuneration for completion of the baseline survey, and \$15 in remuneration for completion of the post-3RP and follow-up surveys (up to \$45 total). Participants will receive \$15 in remuneration for completion of the baseline and follow-up hair sample(s) (up to \$30 total). As required for compliance with Partners Healthcare remuneration policy, we will collect participants' contact information (see Remuneration Form in Appendix 8.13).

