6.3 Stratification factors and intervention allocation plan for randomized studies. N/A

6.5 Stratification factors and their impact on design. N/A

6.6 Early stopping rules, if appropriate. N/A

6.7 Definition of and allowance in design for unevaluable/ineligible participants. No unevaluable and/or ineligible participants will be included in this study.

6.8 Analysis Plan.

Aim a) To examine the feasibility and acceptability of a group-based, stress-management and resiliency intervention delivered via videoconferencing technology for lymphoma survivors who are within 2 years of having completed cancer treatment.

Descriptive statistics, including means, frequencies, and ranges will be used to describe the sample and to summarize feasibility, acceptability, and program satisfaction. Feasibility outcomes will be assessed by determining the proportion of individuals who were recruited, screened, and enrolled in the study. Response frequencies will summarize reasons for ineligibility and refusal. We will also determine the proportion of enrolled participants who complete the study. Participants who complete at least 75% of the treatment sessions (6 out of 8 sessions) will be identified as treatment completers. We will examine the proportion of individuals who attend each session as well as the percent who adhered to recommended relaxation practice (defined as RR

elicitation at least 3 days/week, as measured by the RR practice logs (Appendix 8.3). For acceptability, response frequencies will summarize quantitative feedback on the 3RP Acceptability Questionnaire (Appendix 8.5).

Aim b) To explore the feasibility and acceptability of collecting hair samples to examine changes in stress reactivity.

Feasibility metrics for the hair sampling include hair return rates. For measures of acceptability, response frequencies will summarize quantitative feedback from question 13 on the 3RP Acceptability Questionnaire (Appendix 8.5) about the acceptability of hair collection procedures. Together with qualitative feedback from the Exit Interviews (Appendix 8.7), this information will be used to inform the feasibility and acceptability of hair cortisol measurement. Hair cortisol samples will be analyzed by [name] laboratory at the University of Massachusetts, Amherst. Pearson correlation or Spearman's rank correlation will be used to examine the association of hair cortisol with each of our exploratory psychosocial outcomes.

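### The hair-care and exercise answers are collected because they can affect hair cortisol, and treated or dyed hair is admitted, but the planned cortisol correlations use neither

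*Combined protocol and SAP*

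**What the plan says.** Under Hair Cortisol Measurement, section 5.2 asks donors about possible influences on the assay and gives the reason: "The hair sampling instructions also include 6 questions about hair care, exercise, and glucocorticoid use, as these can affect hair cortisol measurements". It then handles two influences differently. Recent steroid use bars sampling: "Hair samples will not be collected from participants who have taken glucocorticoid medications (e.g. prednisone) within the past 3 months". Cosmetic treatment does not: "However, hair that is chemically treated or dyed may still be used for hair cortisol analysis". Samples are due twice: "Participants will be instructed to provide one hair sample at baseline and one sample at the one-month follow-up". Donation is optional under section 5.5.3: "Participants can still remain in the study if they do not wish to complete a hair cortisol sample".

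Section 6.8 Aim b gives the only analysis of the cortisol values: "Pearson correlation or Spearman's rank correlation will be used to examine the association of hair cortisol with each of our exploratory psychosocial outcomes". It names no covariate, stratum or sensitivity analysis, and does not say at which time point the correlation is taken. The rest of section 6.8 and the missing-data plan in section 6.9 do not mention the hair-care, dye or exercise answers.

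**The concern.** The protocol names influences on its own measurement, asks about them, and then leaves the answers out of the analysis. Two consequences are possible.

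- **Noise.** A factor that shifts cortisol but is unrelated to the psychosocial score widens the spread of cortisol and pulls every correlation towards zero. Hair treatment or dye is the likelier example.
- **Confounding.** A factor related to both cortisol and the score produces a correlation where none exists, or masks a real one. Exercise is the likelier example, because the outcomes include fatigue, depressed mood and anxiety, which may go with how much a person exercises.

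Cortisol is to be correlated with the psychosocial outcomes one by one, and the section 5.4 table lists 13 instruments, so one unadjusted factor can touch several results. The exercise questions were removed from the weekly practice logs (section 5.2, Feasibility). The hair questions are therefore the only exercise data that the supplied text describes.

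**Working it through.** **The plan's own figure.** The only power statement (section 6.2) concerns session attendance: n = 30, a 5.5-point margin, SD 10, one-sided 5%. The noncentrality is 5.5/10 × √30 = 3.01, which gives 90.3% power by the t-test and 91.4% by the normal approximation. The stated 90% is reproduced, but it has no bearing on cortisol. The documents give no sample size, variance or expected correlation for the hair analysis, so everything below is an illustration.

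**Assumptions, none from the documents.** A yes/no factor has prevalence p = 0.3 to 0.5 and shifts log cortisol by d = 0.5 to 1.0 residual SD. The correlation between the factor and the psychosocial score is 0.3. There are 25 donors; section 5.1 expects about 40 people in the program, and hair is optional.

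**1. Attenuation, factor unrelated to the score.** Multiplier = 1/√(1 + p(1−p)d²).
- p = 0.3, d = 0.5: 1/√1.0525 = 0.975.
- p = 0.5, d = 1.0: 1/√1.25 = 0.894.

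The shrinkage is about 3% to 11%. A true correlation of 0.30 becomes 0.30 × 0.975 = 0.292 to 0.30 × 0.894 = 0.268.

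**2. Spurious correlation, factor related to the score, true correlation zero.** r = 0.3 × √[p(1−p)d² / (1 + p(1−p)d²)], with p = 0.4.
- d = 0.5: 0.3 × √(0.06/1.06) = 0.07.
- d = 1.0: 0.3 × √(0.24/1.24) = 0.13.

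Over a wider range, a covariate correlated 0.2 to 0.5 with both variables induces 0.2 × 0.2 = 0.04 to 0.5 × 0.5 = 0.25.

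**3. Cost of adjusting.** The standard error on the Fisher z scale is 1/√(n − 3 − k) for k covariates. This is the Pearson form, used here as an approximation for Spearman.
- n = 25, k = 0: 1/√22 = 0.213.
- n = 25, k = 2: 1/√20 = 0.224, about 5% larger.
- n = 25, k = 3: 1/√19 = 0.229, about 8% larger.

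95% intervals around an observed correlation of 0.30:

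| Donors | No covariates | Two covariates |
|---|---|---|
| 20 | −0.16 to 0.66 | −0.19 to 0.67 |
| 30 | −0.07 to 0.60 | −0.08 to 0.61 |
| 40 | −0.01 to 0.56 | −0.02 to 0.57 |

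**4. Cost of excluding treated hair.** If 40% of 25 samples are treated, 25 × 0.6 = 15 remain. The standard error is 1/√12 = 0.289, about 35% above 0.213. This run is therefore only a check on direction and rough size.

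**The case against.** The strongest reply is that this is a description within a pilot. Aim b asks whether hair can be collected acceptably, judged by return rates, a questionnaire item and exit interviews. Section 6.2 calls the phase exploratory, and section 6.8 leaves planned tests of intervention effects to a later trial. With 25 donors, a spurious correlation of 0.07 to 0.13 is 0.07/0.213 = 0.3 to 0.13/0.213 = 0.6 of a standard error, so adjusted and unadjusted results could hardly be told apart. Admitting dyed hair is also an explicit decision, not an oversight, and the protocol says only that these factors can affect the measurement. All of this stands, and it limits the importance of the point. It does not give the collected answers a use.

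A second reply concerns exercise. The program promotes healthy lifestyle behaviors (section 1.2) and added exercise content after Phase 1 (section 5.3). At follow-up, exercise may lie on the path from the program to cortisol and mood, and adjusting for it could remove real signal. This stands and shapes the fix.

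Three stronger readings are tempting, and the documents do not support them:
- **That steroid use is ignored.** Use in the past 3 months is controlled by restriction, before any correlation is run.
- **That a cortisol change analysis is contaminated by changing hair care.** Change is a stated purpose of sampling, but section 6.8 specifies no baseline-to-follow-up cortisol comparison.
- **That every donor answers the six questions at both samples.** They sit in the sampling instructions, so this is plausible, but the text does not say so and the section 5.4 table does not list them.

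**Conclusion.** The gap is real but minor. The plan identifies hair care and exercise as possible influences on cortisol, admits treated or dyed hair, and then correlates cortisol with the psychosocial outcomes without using that information. Under the stated assumptions the distortion is a 3% to 11% shrinkage, or a spurious correlation of about 0.07 to 0.13. It reaches 0.25 only if a factor correlates 0.5 with both variables. Prevalence, shift, correlation with the score and number of donors are all assumed. The effect is probably small, the component is optional and exploratory, and no go/no-go decision depends on it. A reader should not infer that the planned correlations are invalid; they are a defensible description that can be improved at little cost.

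**What to change.** In section 6.8 Aim b:
- Keep the planned correlations.
- Report beside them partial Spearman correlations adjusted for hair treatment or dye (one yes/no indicator) and exercise, both taken from the six questions.
- Add a sensitivity analysis that excludes chemically treated or dyed samples.
- Label the exercise-adjusted result at follow-up as supplementary, because exercise may be on the program's pathway.

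Stating this in advance also avoids choosing adjustments after the data are seen.

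The cost is a few sentences of analysis text, about two degrees of freedom, and a smaller sample in the sensitivity run. The wording of the six questions (Appendix 8.8) is not in the supplied text, so this assumes that they record treatment or dye and exercise in usable form. The covariates should be defined from the form itself.

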5.3 Description of the Intervention

In Phase 1 of this study (DF/HCC 16-396), qualitative interviews were conducted with up to 20 lymphoma survivors who were less than 2 years post-treatment completion to explore their needs for additional

program content (e.g., treatment-related effects, coping with uncertainty, “reintegrating” into social networks). Phase I participants reported loss of support after treatment completion, fear of cancer recurrence or a new type of cancer, and lack of opportunities to meet other survivors of a similar age as significant areas of concern. Participants endorsed that a group program with other survivors would be helpful, and they also believed that RR techniques could help them cope with uncertainty and loss of support after treatment completion, providing support that the 3RP would meet these survivors’ unmet needs. Participants also expressed a desire to gain information about the ways in which stress, nutrition, sleep, and exercise affect the body, particularly in relation to cancer. As such, we have incorporated additional information on these topics specific to cancer survivors into the 3RP sessions manual. In addition, participants endorsed hair cortisol as an acceptable method of cortisol sampling and expressed that they would be interested in providing hair samples to learn more about their change in stress levels.

The 3RP will thus be delivered in weekly sessions over the course of approximately 8 weeks, for a total of 8 sessions which are approximately 90 minutes each. Modeled after the central tenets of the 3RP,¹ each session includes repetition of core components, which include: 1) 10-point analogue scales of stress, distress, and coping (resembles distress thermometer), 2) weekly goal check-ins, 3) RR-practice, and 4) mini relaxation practice. Participants will learn a new RR strategy at each session that will be based on identified mind-body interests, maximizing the likelihood of finding a technique that is helpful for them. Throughout treatment, participants will be encouraged to practice RR strategies at home for at least 10-20 minutes each day, and they will be asked to document the frequency and duration of practice in weekly practice logs (Appendix 8.3) to record RR adherence. Participants will receive the 3RP patient manual, which describes the content of the 3RP sessions, and RR-based guided meditation CDs or audio files to help them elicit the RR at home each day. The CDs that guide the subject through the procedures have been used in other clinical research studies and clinical practice. It introduces a relaxation sequence to help participants elicit the RR, including some of the key elements such as breath awareness, body scan and use of a focus word, while instructing the participant to passively ignore intrusive thoughts. Additional treatment components based on the 3RP model (Figure 1) and identified qualitative interview themes include coping logs that provide examples drawn from common transitional challenges identified by survivors in the Phase 1 interviews, which will facilitate discussion and practice of restructuring and positive reframing techniques. Lastly, social and educational topics identified in Phase 1 will be interwoven throughout the program and used to guide survivors in applying learned skills (e.g., identifying types of social support needed and developing strategies to facilitate outreach and connection). At the end of each session, the interventionist will complete a process form indicating the length, location and content of the session. We will also collect total number and timing of sessions per participant. The topics addressed in each of the eight 3RP sessions are described in Appendix 8.9.

5.4 Data Collection and Storage.

Prior to study enrollment, study data will be collected via medical record review at screening to determine study eligibility. In addition, we will gather descriptive information about our sample via brief surveys and assess levels of the stress hormone cortisol via hair sample collection. Specifically, we will collect data on:

Data	At Screening	At Baseline	At 3RP	At Post-3RP	At 1-Month Follow-Up
Date of birth	x				
Gender	x				
Languages spoken	x				
Cancer diagnosis	x				
Date of diagnosis	x				

Data	At Screening	At Baseline	At 3RP	At Post-3RP	At 1-Month Follow-Up
Treatment type(s)	x				
Date of treatment completion	x				
Demographic factors		x			
Psychosocial measures:					
Distress Tolerance Scale (DTS)		x		x	x
Measure of Current Status Part A (MOCS-A)		x		x	x
Center for the Epidemiological Studies of Depression Short Form (CES-D-10)		x		x	x
Cognitive and Affective Mindfulness Scale – Revised (CAMS-R)		x		x	x
Assessment of Survivor Concerns Scale (ASC)		x		x	x
Mishel Uncertainty in Illness Scale Community Sample (MUIS-C)		x		x	x
Fatigue Symptom Inventory (FSI)		x		x	x
Life Orientation Test – Revised (LOT-R)		x		x	x
Pittsburgh Sleep Quality Index (PSQI)		x		x	x
Visual Analogue Scale 0-10		x		x	x
Generalized Anxiety Disorder 7-item scale (GAD-7)		x		x	x
Intolerance of Uncertainty Scale – Short Form (IUS-12)		x		x	x
General Self-Efficacy Scale (GSE)		x		x	x
Hair cortisol measurement		x			x
Health services utilization questionnaire		x		x	x
3RP acceptability questionnaire					x
3RP session evaluation surveys			x		
Weekly RR practice logs			x		

To safeguard participant information and confidentiality, all data will be stored in locked cabinets at MGH as well as in password-protected computer files, accessible only to trained and IRB-approved study staff. Participants' data will be identified by an ID number only, and a link between names and ID numbers will be kept separately under lock and key or in a separate password protected document accessible only by study staff. Data identified by ID numbers (de-identified) may also be stored in REDCap, a secure, web-based application designed to support data capture for research studies. Transcripts of all exit interviews will be de-identified, and participants will be directed to avoid using personal identifiers (i.e., birthdays, home address, full names) during the course of the interview, thus maintaining patient anonymity and confidentiality during the interview. Audio-

records of these interviews will be uploaded to our study access-restricted drive. Interviews will either be transcribed by research study staff or be sent securely and transcribed by transcribeme.com.

5.5 Description of Study Process

5.5.1 Instrument Administration

The Baseline, Post-3RP, and Follow-up Questionnaires will be self-administered by participants either on paper or electronically via REDCap survey in accordance with patient preferences. Patients may also elect to complete the questionnaires at home and mail them back to the study staff, or complete them with a member of study staff over the phone or in clinic. Participants may complete the Baseline questionnaire approximately 1-3 weeks prior to the first 3RP session. Participants who have not completed the baseline questionnaire at 1 week prior to the first 3RP session will be instructed by study staff to complete it as soon as possible. The Post-3RP questionnaire may be completed up to approximately 2 weeks after the final 3RP session, and the Follow-up questionnaire may be completed approximately 4-6 weeks after the final 3RP session.

After each weekly 3RP session, a 3RP session evaluation survey will be sent electronically via REDCap to each participant's preferred email address. Participants may choose whether to complete the survey to provide feedback on the 3RP session. In addition, as part of the standard 3RP program, participants will be asked to complete weekly RR practice logs (Appendix 8.3) to record their RR elicitation throughout the week. These will be completed online via REDCap survey or on paper.

Hair Cortisol: Similar to other studies which have utilized hair sample collection for cortisol measurement (Partners IRB Protocol#: 2016P001622), participants will be asked to cut a small amount of hair (approximately 150 strands, which is about the diameter of a pencil eraser) as close to the scalp as possible (about 3 cm), and from the back of their head. They will be asked to band or tie the strands near the scalp end, place on the sample in aluminum foil, and return in an envelope to MGH. Participants will be sent detailed sampling instructions (Appendix 8.8) and stamped, addressed envelopes to facilitate mailing. A member of study staff will review the sampling procedures in detail with participants either in-person at MGH or during the brief test call, according to patient preferences and availability. Participants will be asked to provide hair samples at baseline and one-month follow-up (1-3 weeks prior to the first 3RP session and 4-6 weeks after the final 3RP session, respectively). Participants will also be provided with the Hair Cortisol Results Form (Appendix 8.14), which will give participants the option to receive the results of their hair cortisol levels via a phone conversation with the study PI, which will be scheduled after the completion of the 1 month follow-up.

Qualitative exit interview: After completion of the one month follow-up survey, a member of the study staff will contact participants to see if they would like to complete a qualitative exit interview to provide feedback on the 3RP program and study procedures. Interviews may be conducted via phone, Partners Telehealth videoconferencing software, or in-person at MGH, according to patient preferences and availability. A member of the study team trained in qualitative interviewing will facilitate the interviews in-person, via telephone or Skype using a semi-structured interview guide with open-ended questions and response probes (see Appendix 8.7), and they will last approximately 20 minutes. All interviews will be audio-recorded; study staff will ask for permission to turn on the audio-recorder prior to beginning each interview.

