2.0 OBJECTIVES

Primary aim:

- a) We will conduct a single-arm feasibility trial to examine the feasibility and acceptability of delivering a group-based stress-management program delivered via videoconference technology for approximately 55 lymphoma survivors who are less than 2 years post-treatment. Specifically, we will assess whether a virtually-delivered, 8-week resiliency group intervention for survivors of lymphoma cancers is: **a1) Feasible** (assessed by evaluating recruitment and enrollment rates, adherence to session and relaxation response (RR) practice) and **a2) Well accepted** (defined by program satisfaction, ease and utility).

Secondary aims:

- b) We will explore the feasibility and acceptability of collecting hair samples to examine intervention-related changes in cortisol, a stress biomarker.
- c) We will examine the preliminary effects of the intervention on psychosocial measures of fatigue, mindfulness, depressed mood, anxiety, and stress. (exploratory)

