5.0 STUDY DESIGN AND METHODS

5.1 Design / Study Type

This is a single-arm feasibility trial to examine the feasibility and acceptability of the 3RP among approximately 55 lymphoma survivors who are less than 2 years post-treatment. Participants who sign informed consent but who are found to be ineligible during the brief test call; those who do not complete any study

measures; and those who withdraw or are removed from the study prior to participating in any 3RP group sessions will not be counted towards the accrual goal of 55 participants. As such, up to 55 participants may be enrolled in the study in order to allow approximately 40 patients to participate in the 3RP. We will keep a detailed log of these instances, as this will inform the feasibility of the study. Participants do not need to complete every study measure to be counted towards the 55 accrual goal (participants who only complete some measures/3RP sessions will still be counted towards the accrual goal); however, patients who do not complete any of the study measures or who do not participate in any 3RP sessions will not be counted towards this goal.

All patients, regardless of whether they are counted towards the 55 accrual goal, will be included in the feasibility assessment. We plan to examine the proportion of patients who are eligible and the proportion who are found to be ineligible due to age, language, inability to use the videoconferencing software, oncologist refusal, and medically or psychiatrically unable to participate. Out of those who are eligible, we will examine the proportion of enrollments, refusals, lost-to-follow up, withdraws, and study completers. We will examine reasons for and rates of ineligibility, as these will inform the feasibility of the study and of delivering the program virtually. We will also examine the characteristics of non-completers and the reasons for non-completion.

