Rationale for hair cortisol versus salivary cortisol. Recent studies comparing salivary vs. hair cortisol have found that hair samples provide a more robust measure of chronic stress.³² Specifically, hair cortisol provides a more complete snapshot of cortisol concentration levels across longer periods (e.g., over 2 months) whereas salivary cortisol captures the acute stress response.²⁹ As such, studies have been more likely to find changes in hair cortisol levels in response to stress management programs.²⁹ Further, hair sampling may be less burdensome, invasive, and easier to collect than saliva sampling, which requires subjects to provide several samples throughout the day. Saliva sampling is also subject to sampling errors due to incorrect timing, inefficient sampling, and inaccurate collection procedures.²⁹ We will collect feedback and perceptions of hair sampling measures at study completion. Hair cortisol collection was endorsed as an acceptable sampling method by participants interviewed during in Phase 1 of this study. **Sample Processing:** Hair cortisol will be processed by [name] laboratory at the University of Massachusetts, Amherst. Prior to shipping, samples will remain wrapped in aluminum foil, labeled with a study ID and stored at room temperature in a padded envelope.

Psychosocial Measures (EXPLORATORY OUTCOMES): The following self-report measures (Appendix 8.2) will be administered during baseline, post-3RP, and follow-up data collection periods. It is estimated that these measures will take approximately 30-35 minutes to complete.

- **Distress Tolerance Scale (DTS):** The DTS is a validated, 15-item measure of emotional distress tolerance. Items are rated on a 5-point Likert scale (5=Strongly disagree to 1=Strongly agree), with higher scores corresponding to greater levels of distress tolerance.³³
- **Measure of Current Status – Part A (MOCS-A):** The MOCS-A is a 13-item self-report measure of perceived ability to cope with stress. Each item lists a technique for dealing with daily stressors, with responses ranging from 0 (I cannot do this at all) to 4 (I can do this extremely well). The MOCS-A has

been successfully used to document change in participants' ability to decrease the stress response, another element of the 3RP model.³⁴⁻³⁶

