Exploratory Aim c) We will examine the preliminary effects of the intervention on psychosocial measures of fatigue, mindfulness, depressed mood, anxiety, and stress.

Preliminary outcome data may be used to inform future assessment instruments and methods. We may also conduct exploratory hypothesis testing to examine preliminary changes in our proposed intervention targets (changes in fatigue, mindfulness, depressed mood, anxiety, stress). A priori statistical tests of intervention-related changes will be planned for a future efficacy trial of this intervention. We will compare baseline demographic and clinical characteristics between completers and non-completers using chi square tests and t-tests. Paired samples T-tests will be used to examine pre and post-intervention differences (T2 vs T1) at $p < .05$ for each of our exploratory outcomes (e.g. CAMS-R). We will also assess the sustained effects of treatment with a repeated measures ANOVA analysis, including the 3 survey time points. This analysis will allow us to assess if there is a trend towards maintenance of treatment effects but is not powered to detect significant differences.

Exit interviews (Appendix 8.7) will be audio-recorded and transcribed; NVIVO software will be utilized in the thematic analysis, which will be led by [name] and the study RA under the mentorship of [name], who directs the Qualitative Research Core at MGH. [name] and the study RA will meet on a weekly basis to discuss the coding framework, categories, and coding plan. To ensure coding reliability, coding discrepancies will be resolved through discussion and comparison of raw data. Coding will continue until a high level of reliability ($\text{Kappa} = > 0.80$) is established.

6.9 Handing of missing data in the analysis.

This phase of the study is intended to test the feasibility and acceptability of the stress management program. We will explore differences between study completers and non-completers on patient demographic and other relevant variables to inform the next phase of this trial. We will assess whether the mechanism of missing data is missing at random. We will perform sensitivity analysis using: 1) a completer analysis limited to those who have complete data and 2) multiple imputations for missing data.⁶⁰ To address missing data at follow-up, participants who are no longer interested in participating in the 3RP sessions will still be given the option to complete follow-up assessments.

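### Section 5.5.1 lets survey mode change between waves without recording it, so a net one-way change could mix with pre-post change in the exploratory Aim c scores

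*Combined protocol and SAP*

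**What the plan says.** Section 5.5.1 states that the three questionnaires "will be self-administered by participants either on paper or electronically via REDCap survey in accordance with patient preferences". It then widens the choice: participants may complete them at home and post them back, "or complete them with a member of study staff over the phone or in clinic". No sentence links the mode at one wave to the mode at another.

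Section 5.2 says that the psychosocial self-report measures "will be administered during baseline, post-3RP, and follow-up data collection periods". They include depressive symptoms, anxiety, stress, coping and self-efficacy.

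In section 6.8, exploratory Aim c: "Paired samples T-tests will be used to examine pre and post-intervention differences", at p < .05 for each exploratory outcome, followed by a repeated measures ANOVA over the three survey time points. No term for mode is described. The sensitivity analyses in section 6.9 concern missing data only.

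Section 5.1: "This is a single-arm feasibility trial to examine the feasibility and acceptability of the 3RP". There is no comparison group.

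**The concern.** Answers about low mood, worry or coping may differ according to whether a person fills in a form privately or gives the answers to a member of staff. If participants use one mode at baseline and another later, and more move in one direction than the other, the average score can shift with no change in the participants.

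A control arm surveyed in the same way would tend to share that shift, so that it largely cancelled in the comparison. Here nothing would cancel it: the change of mode coincides with the passage of time, and the paired test and the ANOVA would count it as change. The shift could imitate benefit or hide it. If mode was not recorded at the time, it may not be possible to separate the two later.

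What is at stake is how the preliminary Aim c estimates are read. No primary endpoint depends on pre-post score change.

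**Working it through.** **The plan's own figure.** The only power statement (section 6.2) concerns session participation: n = 30, difference 5.5 points, SD 10, one-sided 0.05. The standardised difference is 5.5/(10/√30) = 3.01. The noncentral t gives 90.3% and the normal approximation 91.4%, so the stated 90% reproduces. It has no bearing on this point.

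**Inputs from the documents.** About 40 participants are expected to take part in the program (section 5.1). The paired test of Post-3RP against baseline is at 0.05 (section 6.8), taken here as two-sided.

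**Inputs assumed, because the documents give none.** Between-wave correlation r = 0.6; net share of participants changing mode in one direction, f; mode effect m, in SD units of the score; no true change.

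**Formulas.**
- Bias in mean change = f × m.
- SE of mean change = √(2(1 − r)/n) = √(0.8/40) = 0.141 SD.
- False-positive rate = P(|Z + bias/SE| > 1.96).

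| Net switching f | Mode effect m | Bias (SD) | Bias/SE | False-positive rate |
|---|---|---|---|---|
| 0% | any | 0 | 0 | 5.0% |
| 10% | 0.2 | 0.02 | 0.14 | 5.2% |
| 20% | 0.3 | 0.06 | 0.42 | 7.1% |
| 30% | 0.5 | 0.15 | 1.06 | 18.5% |

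**Sensitivity of these figures.**
- *t-test in place of the normal.* Switching by only some participants also adds f(1 − f)m² to the variance of change. In the last row that gives 0.8 + 0.21 × 0.25 = 0.8525, and a paired t-test with 39 degrees of freedom then gives about 17%. The third row becomes about 7.0%, and the second stays at 5.2%.
- *Correlation.* With r = 0.4 the SE is √(1.2/40) = 0.173, and with r = 0.8 it is √(0.4/40) = 0.100. The third row then runs from 6.4% to 9.2%, and the last from 13.9% to 32.3%.
- *Fewer pairs.* Forty is the number expected to join the program, not the number with both surveys. With 30 pairs and r = 0.6 the SE is √(0.8/30) = 0.163, and the last two rows fall to 6.6% and 15.1%.
- *Balanced switching.* If equal numbers move each way, the mean bias is zero and only the variance of change rises, by the factor 1 + f m²/0.8, where f is now the total share switching. That is 1.01 for 25% and 0.2 SD, and 1.16 for 50% and 0.5 SD.

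**The case against.** The strongest reply is that the text permits the problem but does not show it. Self-completion is the default. Bias needs participants to switch, the switching to run mainly one way, and a real mode effect, and the documents give no figure for any of these. That stands, and it is why the point is conditional and the range starts at no effect. A 30% net movement away from the default is a strong assumption.

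Some stronger readings are tempting, and the documents do not support them:
- *That mode is known to go unrecorded.* A reader might infer this from the data table in section 5.4. That table lists study measures rather than administrative data, and it also omits items the protocol plainly collects, such as the interventionist's process form and the exit interviews. The appendices with the forms are not in the supplied text, so a mode field on them cannot be ruled out.
- *That staff-assisted answers are always spoken.* This is clear only for the phone. In clinic, a participant might fill in a paper form with staff nearby.
- *That growing familiarity with staff pushes later answers one way.* Participants already meet study staff at screening, consent and the test call before the program, and nothing says that those who lead sessions also administer surveys.
- *That the primary results are at risk.* Enrolment and attendance do not depend on survey mode. The acceptability questionnaire is given once, so it has no pre-post change to distort.

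It is also fair to say that Aim c is exploratory, that section 6.2 disclaims power to detect an effect, and that flexible modes protect survey completion, which is itself a feasibility measure in section 5.2. These points limit the importance of the concern and shape the remedy. They do not remove the gap: within-person tests at p < .05 are planned, and no supplied passage controls or uses mode.

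**Conclusion.** The concern holds in conditional form, as a minor improvement. Section 5.5.1 allows mode to differ between waves, no supplied passage holds it constant, provides for recording it or analyses it, and there is no control arm to absorb a shift. A net one-way change of mode could therefore mix with change in the exploratory mood, anxiety, stress and coping scores.

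The size is unknown. Under the stated assumptions the false-positive rate lies between 5% (no net switching) and about 18% (30% net switching and 0.5 SD), and the documents favour no point in that range. They do not support a conclusion that the Aim c results will be biased.

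**What to change.** - **Section 5.5.1:** keep every mode available, but at Post-3RP and follow-up offer first the mode the participant used at baseline.
- **Data collection (section 5.4 and REDCap):** record at each wave whether the survey was self-completed or staff-read.
- **Section 6.8, Aim c:** report how many participants changed mode and in which direction, and repeat the change estimates in pairs with the same mode at both waves. Label this a descriptive sensitivity check.

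The cost is one field per wave, a sentence or two of text and one extra analysis. Staff must check the earlier mode before offering a survey. The same-mode subset is smaller and may be selected, so it should be read beside the full analysis and not in place of it. If few participants switch, the two will nearly coincide, and the record will show that mode was not a problem. Because no mode is withdrawn, survey completion should not suffer.
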